2. Summary of study procedures – cont-d

Period	Visit	Day	Planned time (relative to drug administration) [h:min]	Approximate clock time of actual day [h:min] ²⁶	Event and comment ¹⁶	Spirometry ^{3,25}	Medical examination	12-lead ECG	Vital signs (BP, PR)	Safety lab ^{19,20,21,22}
			24:45	08:45						
			25:00	09:00	Bolus MCh challenge⁹	X ¹⁸		X	X	
			25:30	09:30						
			26:00	10:00	250mL water intake, thereafter breakfast					
			27:00	11:00						
			28:00	12:00	250mL water intake, thereafter lunch					
			32:00	16:00	snack (voluntary)					
			33:00	17:00	Discharge from trial site			X	X	X ²¹
End of Treatment	6	+14 ^{6,27,15}			End of trial (EOT) examination ¹⁵	X	X	X	X	X

Guidance Notes

1	All subjects must sign an informed consent consistent with ICH-GCP guidelines prior to participation in the trial, which includes medication washout and restrictions.
2	Screening within 14 days before drug administration including review of inclusion and exclusion criteria, relevant medical history, demographics, concomitant medication, physical examination and review of vital signs/ECG/laboratory, Flexibility in scheduling and repeating screening or baseline procedures according to investigator judgement is permitted. Patient's consent can be obtained prior to the screening period.
3	
Spirometry is performed at the screening visit (Visit 1) and Treatment period 1 – Day 1 to determine eligibility for participation in the study.
 
Treatment Periods 2 to 4 – Day 1, eligibility to dose based on the predose FEV % of predicted will be assessed by clinical judgment of the investigator.
 
Prior to methacholine challenge the subject's FEV₁ should be within the range (\geq 70% of predicted normal*) on Day -2 to Day -1 and at Day 2 at Visits 2-5 (Treatment Periods 1 to 4)
 
*Clinical judgement may be applied in borderline cases.

4	
5	Timepoint included for technical (database set-up) reasons only
6	AEs and changes in concomitant therapies will be monitored and recorded throughout the trial
7	Incremental MCh challenge during Visit 1 will use an escalation protocol to determine the PD20 in a given volunteer.
8	In exceptional circumstances, the washout between the two treatment periods can be extended up to a maximum of 8 weeks

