18	Spirometry to be performed pre-MCh challenge, post-diluent and post methacholine dose. Post-methacholine spirometry (FEV ₁ only) timepoints will be relative to the last exhalation of methacholine solution and will be scheduled as single measurements at 30 seconds and 90 seconds, followed by duplicate measurements (FEV1 and FVC) at 5,10, 20, 30,45 minutes, 1.0, 1.25, 1.5, 1.75, 2.0, 2.25, 2.5, 2.75, 3.0, 3.5, 4.0, 4.5, 5.0, 6.0, 7.0 and 8.0 hours
19	Central laboratory: Central laboratory testing (full laboratory screen) will be performed at the screening visit (Visit 1) and on completion of the study (EOT visit / Visit 6). Details of the tests required are provided in Section 5.3.3 .
20	For female subjects: Blood HCG will be performed at screening to confirm eligibility (central laboratory)
21	Electrolytes will be measured prior to start of trial procedures and prior to discharge from the clinic on conclusion of trial procedures at each of the treatment periods (Visits 2 to 5). Initial assessment will be performed by local laboratory. In addition to local testing, a sample for electrolytes will also be sent to the central laboratory.
22	If any significant laboratory test abnormalities are detected, specifically liver function tests, the subject should return to the clinic for repeat testing
23	Spirometry to be performed pre-MCh challenge, post-diluent and post-methacholine dose. Post-methacholine spirometry (FEV ₁) timepoints will be relative to the last exhalation of final methacholine solution and will be scheduled as single measurements at 30 seconds and 90 seconds, followed by duplicate measurements (FEV1 and FVC) at 5, 10, 20, 30, 45 minutes, 1.0, 1.25, 1.5, 1.75, 2.0, 2.25, 2.5, 2.75 and 3.0 hours
24	Must be completed within 30 minutes prior to drug administration
25	FEV ₁ and FVC in triplicate, unless otherwise specified
26	The cumulative times specified in the planned time column are for orientation only. Depending on the actual a.m dosing time at the given day, the procedures and observations related to that a.m dosing (such as pre a.m dose and post a.m dose measurements of the same day) have to be adapted respectively.
27	The end of treatment (EOT) visit should be scheduled no earlier than 14 days after the last dose of study medication. In the event of early discontinuation, an additional earlier visit may be scheduled at investigator discretion.

TABLE OF CONTENTS

CLINICAL TRIAL PROTOCOL.....	1
TITLE PAGE.....	1

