- 1 This study (1363.7) will only start once healthy volunteers have been safely administered 100 and 400 µg b.i.d. of BI 443651 for 7days in a separate ongoing study (1363.2) i.e. no stopping criteria have been triggered in 1363.2.
- 2 Only mild, controlled, stable asthma subjects with well-maintained lung function will be included in the study i.e. subjects on prn SABA or low dose inhaled corticosteroid with an $FEV_1 \geq 70\%$ and no recent respiratory tract infection or exacerbation.
- 3 The study will be split into two parts ([see Section 3.1](#)) with an initial pilot (Part 1) to assess for gross adverse effects of BI 443651 on bronchoconstriction after MCh challenge. In Part 1, subjects will receive BI 443651 in a dose ordered fashion with either placebo **or** the lowest dose first followed by the higher doses and placebo (if not taken first). Individual subjects will not be dosed further if individual stopping criteria (including pulmonary function criteria) are triggered. Stopping criteria are described in detail in [Section 3.3.4](#).

The second part of the study (not necessarily dose ordered) will only proceed if no subjects triggered the first three discontinuation criteria following administration of BI 443651 during Part 1.

- 4 The subjects will be closely monitored throughout the treatment period with frequent evaluation of pulmonary function following MCh challenge. Subjects may only be discharged from clinic after medical assessment has been conducted. The subject's FEV_1 must have returned to $\geq 90\%$ of the first set of spirometry measurements performed that day before the subject can be discharged from the clinic. Rescue medication will be provided as required.
- 5 Safety laboratory testing will be performed during the study with a focus on electrolytes ([see Flow Chart](#)). The study will be stopped if, during Part 1 (pilot) at least 2 subjects in the current cohort or treatment period on active drug showed serum potassium levels $\geq 5.5\text{mmol/L}$ in non-haemolysed blood (confirmed by repeat). In Part 2 (main study), the study would be stopped if 4 subjects on active drug (independent of dose level) showed serum potassium levels $\geq 5.5\text{mmol/L}$ in non-haemolysed blood (confirmed by repeat).

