3.3.4 Removal of subject from therapy or assessments

3.3.4.1 Removal of individual subjects

An excessive withdrawal rate can have a severe negative impact on the scientific value of the trial. Every effort should be made to keep subjects in the trial as scheduled. This includes careful subject selection and appropriate explanation of the trial requirements and procedures prior to enrolment as well as an explanation of the consequences of premature withdrawal.

An individual subject is to be withdrawn from trial treatment if:

a	FEV₁ falls ≥ 45% post methacholine challenge from post diluent value If the subject is symptomatic requiring SABA the study physician must be informed and the appropriate assessments taken, regardless of time-point. The PI should be informed of the situation as soon as possible and a decision will then be made by the PI as to whether the subject is to continue to receive MCh challenges at any further visits or be withdrawn.
b	The subject has a confirmed increase in serum potassium of ≥ 5.5 mmol/L in non-haemolysed blood.

Proprietary confidential information © 2017 Boehringer Ingelheim International GmbH or one or more of its affiliated companies

c	The subject shows relevant individual QT prolongation, i.e. a QTcF increase of greater 60 ms from baseline (pre-dose Day 1 of each Treatment Period)) in connection with absolute QT or QTcF greater than 500 ms, which has been confirmed by a repeat ECG recording.
d	The subject has an asthma exacerbation.
e	The subject withdraws consent for trial treatment or trial participation, without the need to justify the decision.
f	The subject needs to take concomitant drugs that interfere with the investigational product or other trial medication
g	The subject can no longer be treated with trial medication for other medical reasons (such as surgery, adverse events, other diseases, or pregnancy)
h	The subject has repeatedly shown to be non-compliant with important trial procedures and, in the opinion of both, the investigator and sponsor representative, is not willing or able to comply with the trial requirements in the future.

If the subject agrees, he/she will undergo the procedures for early treatment discontinuation and follow up as outlined in the [Flow Chart](#) (FC) and [Section 6.2.3](#).

For all subject the reason for withdrawal (e.g. adverse events) must be recorded in the CRF. These data will be included in the trial database and reported.

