6.7 BASELINE, TIME WINDOWS AND CALCULATED VISITS

Baseline is defined as the last measurement before first study drug administration in each treatment period.

For endpoints related to methacholine challenge baseline refers to the measurement obtained from the baseline bolus MCh challenge prior to administration of trial medication within each treatment period. The post-diluent value refers to the last measurement before methacholine administration (i.e. timepoint -0:05 relative to methacholine challenge).

Measurements taken after start of administration of trial medication will be considered on-treatment values or follow-up values, based on the definition of the study analysis phases in Section [6.1](#).

Adherence to time windows will be checked at the BRPM/DBLM.

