7.8.5.2 Pulmonary function tests

Clinically relevant findings in spirometry data (FEV1 and FVC) will be reported as AEs and will be analysed as part of AE analysis.

Descriptive statistics will be provided for FEV1 and FVC obtained at the screening visit based on the TS.

Analyses of further endpoints and parameters of interest related to PFT are described in Section [7.6.1](#).

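### The Day 2 discharge rule measures FEV1 recovery from a reading taken after two doses, so it cannot detect a fall since Day 1 pre-dose; it should use the higher of the two readings

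*Protocol*

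**What the plan says.** Safety measure 4 in Protocol section 2.3 sets two conditions for leaving the clinic. The first is clinical: "Subjects may only be discharged from clinic after medical assessment has been conducted". The second is numerical: FEV1 must be back to at least 90% "of the first set of spirometry measurements performed that day before the subject can be discharged from the clinic". Rescue medication is available.

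The Flow Chart fixes what the first set is on Day 2. Doses are planned at 0:00 and 12:00 on Day 1 and at 24:00 on Day 2. The first Day 2 spirometry is at 23:00, the bolus challenge at 25:00 and discharge at 33:00. Guidance note 18 runs the Day 2 post-methacholine readings out to "3.5, 4.0, 4.5, 5.0, 6.0, 7.0 and 8.0 hours", and the last of these falls at about the planned discharge time.

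A pre-drug reading exists in every period: the Day 1 admission spirometry, taken within two hours before the first dose. No visible text ties Day 2 discharge to it or to a percent-predicted floor. The nearest other number is in guidance note 3, which asks for FEV1 of at least 70% predicted before each challenge and adds: "Clinical judgement may be applied in borderline cases". That governs whether the challenge goes ahead, not whether the subject goes home.

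**The concern.** A recovery rule is only as strict as its reference. If the drug has lowered FEV1 and the fall is still present at 07:00 on Day 2, the reference falls with it. The limit is then lowest for the subject who has reacted most.

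The trial exists to look for harmful effects on lung function in a sensitive population. Protocol sections 1.1 and 2.1 say that bronchoconstriction could in theory occur without a challenge in patients with heightened cholinergic tone. Section 1.2.6 reports a reversible drop in FEV1 and FVC in some healthy volunteers; its size and dose are not visible in the public copy. After Day 2 discharge the Flow Chart schedules no spirometry until the next period's baseline challenge or the end-of-treatment visit, about two weeks later. In Part 2 the assessors are blinded, so they cannot tell whether a low morning value followed active drug.

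**Working it through.** **Limit under the present rule.** Let f be the fractional fall from Day 1 pre-dose to the 23:00 reading. The documents give no value for f, so a range is shown. The limit as a share of Day 1 pre-dose is 0.9 x (1 - f).

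| f | Present limit | Below pre-dose |
|---|---|---|
| 0% | 90.0% | 10.0% |
| 5% | 85.5% | 14.5% |
| 10% | 81.0% | 19.0% |
| 20% | 72.0% | 28.0% |

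**How far the 70% predicted check bounds this.** Suppose the Day 2 value is exactly 70% predicted, the lowest that passes without use of judgement. The discharge limit is then 0.9 x 70 = 63% predicted. Against a limit counted from Day 1 pre-dose:

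- Day 1 at 80% predicted (f = 1 - 70/80 = 12.5%): 63% against 72%.
- Day 1 at 90% predicted (f = 22.2%): 63% against 81%.
- Day 1 at 70% predicted (f = 0): 63% under both.

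**Which reference to use instead.** Day 1 pre-dose alone would weaken the rule whenever the Day 2 morning value is the better one. With Day 1 at 80% and Day 2 at 90% predicted, the present limit is 0.9 x 90 = 81%. Counted from Day 1 alone it would be 0.9 x 80 = 72%. With no drug effect and symmetric variation, the Day 2 value exceeds the Day 1 value in half of all periods. The higher of the two gives 81% here, and 81% in the reverse case of Day 1 at 90% and Day 2 at 80% (present limit 72%). It is never below the present limit.

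**Added first-check failures.** The documents give no within-subject FEV1 variability, so these inputs are assumed: session CV w of 4, 6 or 8%, extra day-to-day CV d of 0, 2 or 4%, normal errors, no drug effect and full recovery from methacholine. Planned discharges: 36 subjects x 4 periods = 144.

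Put true FEV1 at 100. Let X1, X2 and X3 be the Day 1 pre-dose, Day 2 first and discharge readings; X2 and X3 share the same day effect. Define A1 = X3 - 0.9 X1 and A2 = X3 - 0.9 X2. Both have mean 10, and

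- Var(A1) = 1.81 (w² + d²)
- Var(A2) = 1.81 w² + 0.01 d²
- Cov(A1, A2) = w² + 0.1 d²

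The present rule fails when A2 < 0. The higher-of rule fails when A1 or A2 is below 0, a bivariate normal probability. For w = 4 and d = 0, the present rule gives Phi(-10/sqrt(28.96)) = Phi(-1.858) = 0.0316. The new rule, with correlation 16/28.96 = 0.552, gives 0.0557. The difference is 144 x 0.0241 = 3.5.

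| w | Present failures of 144 | Added, d = 0 | Added, d = 2 | Added, d = 4 |
|---|---|---|---|---|
| 4% | about 4.6 | 3.5 | 5.7 | 12.0 |
| 6% | about 15.5 | 9.8 | 11.4 | 15.4 |
| 8% | about 25.4 | 14.1 | 15.1 | 17.5 |

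Some are added even at d = 0, because the higher of two noisy readings is harder to match than one.

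**The case against.** The strongest reply is that the rule does what it was written for. Safety measure 4 is about monitoring after methacholine, and a same-day pre-challenge reference is the natural test of recovery from that challenge. It is also the protocol's own convention. Withdrawal criterion a applies when FEV1 "falls ≥ 45% post methacholine challenge from post diluent value", and both secondary endpoints are anchored to the post-diluent value. SAP section 6.7 does say "Baseline is defined as the last measurement before first study drug administration in each treatment period", but goes straight on to separate definitions for the challenge endpoints. This stands: the reference is not an inconsistency. It leaves one question unasked, namely whether the subject is back to the pre-drug state.

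The second reply is that the premise is thin. The fall would have to persist 11 hours after dose 2 without a challenge. Section 2.3 reports no adverse effect on pulmonary function in animals without a challenge. Someone would probably notice a large fall: spirometry is frequent between doses, SAP section 7.8.5.2 states "Clinically relevant findings in spirometry data (FEV1 and FVC) will be reported as AEs", and withdrawal for an exacerbation or other medical reasons is available. Section 3.1 requires a spirometry review between Part 1 periods and a safety review before Part 2, and the trial starts only after 100 and 400 µg b.i.d. have been given safely in healthy volunteers. All of this stands and limits the weight of the point. None of it supplies a pre-drug FEV1 reference at discharge.

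Two stronger readings should be resisted. A reader might infer that subjects are likely to be sent home with very large falls. The documents give no evidence of this, and a limit of 63% predicted is not in itself treated as unsafe: a subject who enters at 70% predicted has that limit with no drug effect at all. A reader might also infer that the protocol directs sites to continue dosing through a fall in FEV1, because section 4.2.2.2 says scheduled procedures should go ahead. That sentence concerns breaches of the bronchodilator and inhaled-steroid timing restrictions, not falls in FEV1. Nor can the absence of a pre-dose FEV1 rule be asserted, since Flow Chart note 4 is blank in the public copy.

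**Conclusion.** The point holds as a gap in one safety rule. On Day 2 the only visible FEV1 number for discharge is counted from an on-treatment reading, so any fall still present 11 hours after dose 2 lowers the limit in proportion: to 19% below pre-dose for a 10% fall, and 28% below for a 20% fall. The timing and the arithmetic come directly from the text. The size of any such fall in asthma is unknown, and the range for f is an assumption.

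The gap is confined to Day 2 of active periods. On Day -2 or -1 the first reading precedes that period's drug, and in a placebo period there is no drug effect to hide. With the mandatory medical assessment and the other safeguards, this is a low-cost safety improvement worth making, not evidence that the trial is unsafe. It has no bearing on the primary or secondary analyses.

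**What to change.** Amend safety measure 4 so that, on Day 2, FEV1 must have returned to at least 90% of the higher of (i) that treatment period's Day 1 pre-dose FEV1 and (ii) the first FEV1 measured on Day 2. Make the check at the 8.0-hour post-methacholine reading. If it is not met, the subject stays, receives rescue medication if needed and is re-measured. Leave the Day -2/-1 rule unchanged.

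All three readings are already scheduled. The check falls at the last endpoint reading, so rescue given because of it cannot affect the endpoint data. The cost is staff time and some longer stays: about 3.5 to 17.5 more first-check failures over the planned 144 discharges on the assumptions above, each leading to a repeat reading. No hold on doses 2 and 3 is proposed.

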3. DESCRIPTION OF DESIGN AND TRIAL POPULATION

3.1 OVERALL TRIAL DESIGN AND PLAN

This multiple dose, randomised, placebo controlled, trial will be conducted in two parts. The first part (pilot study) will be a single-blind four-way crossover with dose ordered sequences. The second part (main study) will be a double-blind four-way crossover, conducted according to a William's design. In both parts of the study, BI 443651 or placebo equivalent will be administered three consecutive times, 12 hours apart, per dose level. All subjects will receive placebo, 100, 400 and 1200 µg BI 443651 (in Part 1, the dose groups may be altered in case evolving data suggests a change in dosage is required (see below)). Each period will be separated by a washout period of at least 14 days (and not more than 28 days). Two administrations of BI 443651 will be delivered on Day 1 (morning and evening) and a single administration Day 2 (morning). One hour after dosing on Day 2, MCh challenge will be performed. A methacholine challenge will be conducted on Day -2 to Day -1 for each treatment period, (with the Day -2 to Day -1 challenge providing the baseline for each treatment period) at the same time of the day.

The two parts of the study will be conducted as follows:

Part 1: 4 subjects will be included in the first pilot part of the study each being administered three active doses of BI 443651 and placebo, with the active doses investigated being in ascending order of dose strength. Placebo administered given in a single-blinded manner in any order relative to the active treatment as per Table 3.1:1.

Table 3.1:1 Sequences for pilot part of the study

Treatment Period 1	Treatment Period 2	Treatment Period 3	Treatment Period 4
Placebo	100 µg	400 µg	1200 µg
100 µg	Placebo	400 µg	1200 µg
100 µg	400 µg	Placebo	1200 µg
100 µg	400 µg	1200 µg	Placebo

Part 2: 32 subjects will participate in the trial with each subject being administered three active dose levels of BI 443651 and placebo. This part of the study will be fully randomised, double blind. The decision to proceed to Part 2 will be based upon the safety and tolerability data of Part 1. Part 2 will only be conducted if, in the opinion of the investigator, no safety concerns arose in Part 1 and if none of the pre-specified trial-specific stopping criteria were met ([see Section 3.3.4.2](#)).

Table 3.1:2

Sequences for main part of the study

Treatment Period 1	Treatment Period 2	Treatment Period 3	Treatment Period 4
Placebo	100 µg	400 µg	1200 µg
100 µg	Placebo	1200 µg	400 µg
400 µg	1200 µg	Placebo	100 µg
1200 µg	400 µg	100 µg	Placebo

The first pilot part of the study will not be started until data from an ongoing multiple rising dose study (1363.2) in healthy volunteers is available from the first two dose groups (100 and 400 µg b.i.d. BI 443651). Only if BI 443651 has been safely administered in study 1363.2 and no stopping criteria have been met, will this study (1363.7) be started.

In Part 1, dose groups will be investigated consecutively in ascending order of doses with a dose escalation review between each treatment period. Data from each treatment level will be reviewed prior to progression to the next treatment level. Only if the previous dose of BI 443651 is safe and well tolerated, without meeting any stopping criteria in subjects administered BI 443651 ([see Section 3.3.4.1](#)), will the subsequent dose be administered ([Table 3.1:1](#)).

In addition a documented Safety Review by the Coordinating Investigator (or an authorised deputy) and appropriate personnel from the Sponsor must take place prior to initiation of Part 2 of the study. Only if BI 443651 is safe and well tolerated in all subjects in the pilot part without the specified number of subjects meeting any individual stopping criteria (see Section 3.3.4.1), will the transition to Part 2 occur.

An unscheduled safety review meeting can be requested anytime for any reasonable cause by the Principal Investigator (or an authorised deputy) or the sponsor of the study, e.g. because of any unforeseen adverse events, etc. Dose escalation or transition to Part 2 will only be permitted if no safety concerns exist in the opinion of the Principal Investigator (or an authorised deputy) and the Trial Clinical Monitor (or an authorised deputy). The minimum data set for review consists of the following data:

- Results from spirometry in all subjects included in the initial pilot part of the study
- AEs in all subjects including in the initial pilot part of the study, up to at least 48h post dosing (including clinically relevant findings from ancillary safety testing listed below) (Note: AEs may be ongoing at the time of Safety Reviews and AE information may be subject to change prior to Database Lock)
- Check of criteria for stopping subject treatment as per Section 3.3.4.1

Proprietary confidential information © 2017 Boehringer Ingelheim International GmbH or one or more of its affiliated companies

The decision to escalate the dose during the pilot study or transition to Part 2 of the study will be made jointly by the Co-ordinating Investigator (or an authorised deputy) and appropriate personnel from the Sponsor company after in-depth analysis of all available safety data, especially SAEs (if occurred), AEs and out-of-range laboratory results (if considered clinically significant). Safety Reviews can be conducted face-to-face or by video/telephone conference. The Trial Clinical Monitor is responsible for organization and minutes of the reviews. Minutes will be signed off by the Co-ordinating Investigator (or an authorised deputy) and filed in the ISF and TMF.

In the pilot study (Part 1), the investigator is allowed to alter the scheduled dose levels (e.g. add an intermediate dose level) within the planned and approved dose range on the basis of experience gained during the study. In this case, subjects may be required to participate in additional treatment periods or additional subjects may be enrolled. The investigator and/or the sponsor should stop dose escalation in case the safety evaluation leads to concerns that would not allow higher dosing.

An overview of all relevant trial activities is provided in the [Flow Chart](#). For visit schedules and details of trial procedures at selected visits, refer to [Sections 6.1](#) and [6.2](#), respectively.

